### 6.3.1 Study Schedule

For each study, participants will complete an intake visit (approx. 2 hrs). Following intake and eligibility determination, participants will complete the pilot study with a single lab session and the main study with 3 labs sessions, at least 24 hours apart.

### 6.3.2 Informed Consent

At intake, participants will be read informed consent and any questions will be discussed with researcher. Participants will sign informed consent (via Redcap) and consent will be administered by trained research staff.

### 6.3.3 Screening

For the pilot study, we aim to recruit 30 adult participants and for the main study, we aim to recruit 66 adult participants (33 female, 33 male) using online advertisements, community flyering, and referrals. Potential participants will be recruited via the centralized recruitment services provided by the Yale TCORS Administrative Core which involves the use of various recruitment techniques including advertising on social media websites (e.g., Facebook, Instagram, Snapchat, Reddit), at local colleges and jobsites and through Craigslist and flyers in the community, and a clinical trials recruitment company, BuildClinical. PI and/or study research staff will be responsible for contacting participants. Potential participants will be directed to a voluntary link containing brief screening questions including information for research team to contact and/or phone number for participants to contact research staff

directly. If interested, participants will be asked if they regularly use nicotine containing e-cigarettes, and if they are at least 18. If interested, potential participants will be invited to take part in an intake visit to determine eligibility. Intake visits will be completed in person and should take approximately 2 hours.

Participants who fail to be eligible for current medical reasons (e.g., just started a new medication, have an upcoming procedure, or have an ailment that has resolved) or have another temporary ineligibility may be rescreened at a later date. PI will assess in concert with study nurse to determine if they are ok to rescreen. Participants will not be told at any intake why they are not eligible to protect inclusion/exclusion criteria and avoid any deceptive tactics for enrollment.

#### **6.3.4 Enrollment**

If eligibility criteria are met, participant will be enrolled. PI will deem subjects eligible following review and will assign enrolled subject ID.

#### **6.3.5 On Study Visits**

See 6.3 "Study Procedures" above and Table 1.

#### **6.3.6 End of Study and Follow-up**

After completion, participants will be provided with written materials on e-cigarette cessation. Brief follow-up phone calls will take place at 1 month and 6 months after study completion to assess their current tobacco use behavior.

#### **6.3.7 Removal of subjects**

Subjects may withdraw at time voluntarily for any reason. Once participants have signed consent, they may withdraw at any time by communicating to any member of the research team. Any data that has already been collected can still be used, as necessary to ensure the integrity of the study and/or study oversight. Additionally, the research team may decide to withdraw participants if necessary, including if participants do not follow directions of the study team, the study team decides the study is not in a participant's best interest, or if a participant becomes pregnant, intends to become pregnant, or begins nursing a child.

No anticipated adverse events are expected that would require participant withdrawal. Adverse events are not anticipated. In the event that a participant either withdraws from the study or the investigator decides to discontinue a participant due to an adverse event, the participant will be monitored by the investigator via ongoing status assessment until 1) a resolution is reached i.e., the problem requiring hospitalization has resolved or stabilized with no further changes expected 2) the SAE is determined to be clearly unrelated to the study intervention, or 3) the SAE results in death. Outcome of SAEs will be periodically reported to NIDA. A summary of the SAEs that occurred during the previous year will be included in the annual progress report to NIDA. Withdrawal will be documented in a study participant tracker.

### **6.4 Statistical Method**

#### **6.4.1 Statistical Design**

Preliminary analyses will provide an overview of the data (e.g., randomization success, outcome distribution, missingness patterns). Outcome analyses will be intent-to-treat and use mixed-effects models which allow for different numbers of observations/subject, use all available data, and can handle missing-at-random data. If model assumptions will appear to be violated, we will transform the data or fit more flexible generalized linear or nonparametric mixed models. For the pilot study, separate mixed-effects models will examine the influence of different concentrations of menthol, WS-23 and WS-3 on coolness and overall intensity and will be used to select the concentrations of menthol and WS-3 that product the weak but detectable coolness and the maximum coolness. For the main study, separate mixed-effects model will include menthol (0, Concentration 1, Concentration 2), WS-3 (0, Concentration 1, Concentration 2), WS-23 (0, Concentration 1, Concentration 2, Concentration 3) and time within lab as factors, all interactions among those factors and adjust for stratification variables. A combination of random effects and structured variance-covariance matrices will be used to account for within-subject correlations. The best-fitting structure will be selected based on Akaike information criterion (AIC). For the main study, higher liking/wanting for WS-3 (at Concentration 1 or 2) or WS-23 (at Concentration 1 or 2 or 3) combined with menthol (at Concentration 1 or 2), compared to menthol alone, will be supportive of the primary hypothesis. Similar models will examine the other outcomes and interactions of different concentration combinations of WS-3, WS-23 and menthol with nicotine. Exploratory analyses will also consider the impact of sex, combustible tobacco use and nicotine dependence on experiences from WS-3, menthol and nicotine.

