	Concentration 1	Concentration 2	Concentration 3	Concentration 4	Concentration 5	Concentration 6
WS-3 Block	0.05%	0.1%	0.5%	1.0 %	2.0 %	-
WS-23 Block	0.05%	0.1%	0.5%	1.0 %	2.0 %	4.0%
Menthol Block	0.05%	0.1%	0.5%	1.0 %	2.0 %	-

**Table 2.** Main Study Experimental Design

	No WS-3	Low (0.1%) WS-3 Concentration	High (2.0%) WS-3 Concentration	Low (0.1%) WS-23 Concentration	High (2.0%) WS-23 Concentration	4% WS-23 Concentration
Low (0.1%) Menthol	S 1 -S 66					
High (2.0%) Menthol	S 1 -S 66					
No Menthol	S 1 -S 66					

S=Subject. All subjects (1-66) will be exposed to all conditions in the adjacent table.

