**Main Study:** The purpose of the main study will be to determine sensory responses following exposure to e-liquids containing nicotine and WS-3, WS-23, and menthol. This study will recruit 66 adult e-cigarette users (50% with current cigarette use, of which 50% will use menthol cigarettes), to participate in 3 laboratory sessions, separated by at least 24 hrs. At the intake visit, participation in the oral microbiome and inflammatory marker testing will be optional for exclusive e-cigarette users (up to 33). Specifically, they will be asked to provide saliva and urine samples for oral microbiome and inflammatory marker testing and complete a brief survey about their oral health status. Additionally, participants will be asked to submit their most used e-cigarette device/pods from the past-month for analysis. These will be used as exploratory assessments. During the lab visits, participants will receive all eighteen conditions shown in Table 2 below and will be asked to abstain from tobacco use for two hours prior to session start (to control for time since last tobacco exposure). Participants will be randomized to receive one of the 3 menthol conditions (no-menthol, low menthol, high menthol, levels determined by the pilot study above) in Lab 1 and will receive the alternative conditions in randomized order in Lab 2 and Lab 3. During each lab session the menthol condition will be paired with three WS-3 concentrations: no WS-3, low (0.1%) WS-3, or high (2.0%) WS-3 and three WS-23 concentrations: low (0.1%) WS-23, high (2.0%) WS-23, or 4% WS-23 (concentration determined by pilot study) in randomized order. All e-cigarettes will contain nicotine salt at a nicotine concentration of ~59mg/ml, commensurate with levels in popular commercially available nicotine salt e-cigarettes. Each exposure will consist of a 5-puff bout (each puff 3-sec long and separated by 30 sec.) collected via a puff topography device (an apparatus used to measure puffing behavior) and will be separated by 30 mins to allow any sensory effects to dissipate between exposures. To precisely measure puffing behavior, we will utilize a validated electronic cigarette topography device (eTop). This device connects to a computer with software designed to measure puffing behavior. An e-cigarette is inserted into a silicone mouthpiece and the mouthpiece is connected to tubing which feeds into the device. As a participant inhales this device measure puffing behavior including number of puffs, puff volume, puff duration, puff flow rate (a calculation of volume/time). These indices help us understand vaping behavior and make it possible to compare e-cigarette exposure across participants. Topography mouthpieces are sanitized in between subjects and inhaling e-cigarettes via topography devices present no increased risk to participants. At the end of each of the three lab sessions, participants will choose between the 6 e-liquids they sampled in the lab using a free-choice paradigm (~30 mins).

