## 6 Methods

### 6.1 Treatment

#### 6.1.1 Identity of Investigational Product

Products used in this study are investigational tobacco products including 16 different e-liquids and 1 e-cigarette device for the pilot study and 18 different e-liquids and 1 e-cigarette device for the main study. The e-cig device to be used will be the Suorin iShare™ pod device. iShare characteristics resemble the popular JUUL device in terms of power output, shape, and size, but with the benefit of refillable cartridges. The Yale TCORS lab core has demonstrated its near 100%-effectiveness in delivering nicotine to users using a custom-made vaping machine. Nicotine concentrations will be 0 mg/ml in the pilot study and will be 59 mg/ml nicotine salt (nicotine benzoate) in the main study, a widely used and well tolerated nicotine salt formulation and concentration, similar in strength to a 5% JUUL product. PG/VG levels for the study e-liquids will be 50:50 PG/VG, a ratio typical of nicotine salt e-liquids and used in previous studies by our group.

E-liquids will be created upon review of the (Investigational Tobacco Product) ITP application by the FDA; [name] leads Yale TCORS ITP applications and will oversee this process. All e-liquids will be created via the Yale Investigational Drug Service (IDS) Pharmacy under the direction and supervision of [name] (Manager, Investigational Drug Service Pharmacy). E-liquid recipes have been developed via the Yale Laboratory Core and with consultation of [name], a chemist with American E-

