### **6.1.2 Dosage, Administration, Schedule**

Regarding the pilot study, participants will receive two puff exposures to each condition; each exposure will be separated by 10 mins to allow the flavor to dissipate. All e-cigarette pods will be filled to 0.5mL of e-liquid.

Regarding the main study, e-cigarette pods will be filled with approximately 0.9mL of e-liquid, which in previous trials has produced at least 30 puffs. Participants will be randomized to receive one of the 3 menthol conditions (no-menthol, low menthol, high menthol, levels determined by the pilot study above) in Lab 1 and will receive the alternative conditions in randomized order in Lab 2 and Lab 3. During each lab session the menthol condition will be paired with three WS-3 concentrations: no WS-3, low (0.1%) WS-3, or high (2.0%) WS-3 or three WS-23 concentrations: low (0.1%) WS-23, high (2.0%) WS-23, or 4% WS-3 (concentration determined by pilot study) in randomized order. All e-cigarettes will contain nicotine salt at a nicotine concentration of ~59mg/ml, commensurate with levels in popular commercially available nicotine salt e-cigarettes. Each exposure will consist of a 5-puff bout (each puff 3-sec long and separated by 30 sec) via a puff topography a device (an apparatus used to measure puffing behavior) and will be separated by 30 mins to allow any sensory effects to dissipate between exposures. The e-cig pods containing e-liquids will be weighed before and after the session.

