### **6.5 Planned Analyses**

#### **6.5.1 Primary, Secondary, and Exploratory Objective Analysis**

For the pilot study, separate mixed-effects models will examine the influence of 5 different concentrations of menthol and WS-3 on coolness and overall intensity and will be used to select the concentrations of menthol and WS-3 that product the weak but detectable coolness and the maximum coolness. For the main study, separate mixed-effects model will include menthol (0, Concentration 1, Concentration 2), WS-3 (0, Concentration 1, Concentration 2), WS-23 (0, Concentration 1, Concentration 2, Concentration 3), and time within lab as factors, all interactions among those factors and adjust for stratification

variables. A combination of random effects and structured variance-covariance matrices will be used to account for within-subject correlations. The best-fitting structure will be selected based on Akaike information criterion (AIC). For the main study, higher liking/wanting for WS-3 (at Concentrations 1 or 2) or WS-23 (at Concentrations 1 or 2 or 3) combined with menthol (at Concentration 1 or 2), compared to menthol alone, will be supportive of the primary hypothesis. Similar models will examine the other outcomes and interactions of different concentration combinations of WS-3/WS-23 and menthol with nicotine. Exploratory analyses will also consider the impact of sex, combustible tobacco use and nicotine dependence on experiences from WS-3/WS-23, menthol and nicotine.

Oral microbiome and inflammatory marker assessment will serve as another exploratory objective in this study. Microbial testing, including DNA extraction, library preparation and sequencing methods, will be performed at the CosmosID lab. The analysis will evaluate alpha and beta diversity across different flavor-use groups, with the significance of group-wise clustering determined using a permutational multivariate analysis of variance (MANOVA). Statistical methods such as ANOVA, t-tests and chi-square will assess between-group differences, while controlling for nicotine concentration based on total nicotine equivalents measured in urine samples from participants.

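### The main-study model crosses WS-3 with WS-23, but no liquid contains both: every WS-3 × WS-23 term lacks data, while the primary cell contrasts and stated power are unaffected

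*Combined protocol and SAP*

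**What the plan says.** The statistical design in section 6.4.1 names menthol (zero and two concentrations), WS-3 (zero and two concentrations) and "WS-23 (0, Concentration 1, Concentration 2, Concentration 3) and time within lab as factors, all interactions among those factors". Section 6.5.1 gives the same model: "WS-23 (0, Concentration 1, Concentration 2, Concentration 3), and time within lab as factors, all interactions among those factors". Both sections carry similar models over to the other outcomes. The decision rule in 6.5.1 looks for "higher liking/wanting for WS-3 (at Concentrations 1 or 2) or WS-23 (at Concentrations 1 or 2 or 3) combined with menthol", each compared with menthol alone.

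The design is narrower than the model. Table 2 in section 5.1 has three menthol rows and six coolant columns: no coolant, WS-3 low, WS-3 high, WS-23 low, WS-23 high and WS-23 4%. No column holds both coolants. The table note says "All subjects (1-66) will be exposed to all conditions in the adjacent table", and the main-study text says "participants will receive all eighteen conditions shown in Table 2 below". Section 6.1.1 lists "18 different e-liquids and 1 e-cigarette device for the main study". Section 6.3 has six puffing bouts per session, and at the end of a session "participants will choose between the 6 e-liquids they sampled in the lab". Section 6.1.2 joins the two coolant series with or: "high (2.0%) WS-3 or three WS-23 concentrations: low (0.1%) WS-23".

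The objectives are worded more loosely. Sections 4.1 and 4.3 list WS-3, WS-23 and menthol together without saying that the two coolants are never mixed. Section 4.2, read literally, gives each exposure one WS-3 level and one WS-23 level in combination with a menthol level.

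**The concern.** A model with all interactions among three crossed factors presumes that their level combinations were observed. Here half of them never are. The plan therefore promises interaction tests for which there are no observations, and a reader of 4.1 to 4.3 could expect a WS-3 × WS-23 result.

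The second risk lies in factor-level summaries. When software meets empty cells it may decline to estimate an averaged effect, or it may drop redundant columns and print a number whose meaning depends on the coding. The plan does not say which should happen. Section 4.1 also makes a claim about adding menthol, for which neither analysis section defines a contrast, so an analyst may well turn to the printed menthol effect.

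**Working it through.** **1. The plan's own power figure.** Section 6.4.2 gives 60 completers, a difference of 11.4, an SD of paired differences of 25 and alpha 0.01; sidedness is not stated and two-sided is assumed. The noncentrality is (11.4 / 25) × √60 = 0.456 × 7.746 = 3.53 on 59 df, and the noncentral t gives 80.4% power, against 80% stated. The calculation compares two administered liquids, so no empty cell enters it. (6.4.2 also prints alpha as 0.1; that is a separate matter.)

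**2. Cells.** Model: 3 × 3 × 4 = 36. Administered: 3 menthol × (1 none + 2 WS-3 + 3 WS-23) = 18. Empty: 3 menthol × (2 WS-3 × 3 WS-23) = 18, all of them mixtures of both coolants. Section 6.1.2 labels the 4% level WS-3 where Table 2 labels it WS-23; that needs reconciling but does not change the count of 18.

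**3. Rank by term,** time left out, on the 18 administered cells. The result is the same under reference and sum-to-zero coding.

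| Term | Nominal df | Rank added |
|---|---|---|
| Intercept | 1 | 1 |
| Menthol | 2 | 2 |
| WS-3 | 2 | 2 |
| WS-23 | 3 | 3 |
| Menthol × WS-3 | 4 | 4 |
| Menthol × WS-23 | 6 | 6 |
| WS-3 × WS-23 | 6 | 0 |
| Menthol × WS-3 × WS-23 | 12 | 0 |
| Total | 36 | 18 |

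**4. Time.** With T levels of time within lab, the time interactions of the last two terms add 18 × (T − 1) empty df. The plan does not define T. If it means the six bout positions (an assumption), that is 18 × 5 = 90.

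**5. Estimability.** In the stated model a contrast is estimable only if it puts no weight on the 18 empty cells.

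- Estimable: all 10 contrasts of coolant plus menthol with the same menthol alone (5 coolant levels × 2 menthol levels); menthol × WS-3 at WS-23 = 0 (4 df); menthol × WS-23 at WS-3 = 0 (6 df).
- Not estimable: menthol, WS-3 and WS-23 effects, and the menthol two-way interactions, averaged over the full grid. Six of the 12 grid cells at each menthol level are empty.

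**6. The menthol effect if aliased columns are dropped.** Without WS-3 × WS-23 terms, each empty cell is predicted as cell(m, a, 0) + cell(m, 0, b) − cell(m, 0, 0). Sum-to-zero coding averages over the 12 grid cells. Each WS-3 level gets 4/12 = 1/3, each WS-23 level gets 3/12 = 1/4, and no coolant gets 1/3 + 1/4 − 1 = −5/12. Check: −5/12 + 2 × 1/3 + 3 × 1/4 = 1. Reference coding instead puts weight 1 on no coolant. A sum-to-zero six-level coolant factor puts 1/6 on each condition.

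**7. Illustration.** These effects are hypothetical; the documents give none. High menthol adds 10 points with no coolant and x points with any coolant.

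| x | Sum-to-zero, columns dropped: −(5/12)(10) + (17/12)x | At no coolant | Mean of six administered: (10 + 5x)/6 |
|---|---|---|---|
| 10 | 10.0 | 10 | 10.0 |
| 8 | 7.2 | 10 | 8.3 |
| 6 | 4.3 | 10 | 6.7 |
| 4 | 1.5 | 10 | 5.0 |

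For x below 10, the first value lies below every one of the six simple effects, which no average over administered liquids could do. With no interaction (x = 10) the three agree.

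**8. Replacement model.** Menthol crossed with a six-level coolant factor has 1 + 2 + 5 + 10 = 18 parameters and rank 18. Joined to the stated model matrix the rank is still 18, so with time handled identically in both the fitted cell means are the same.

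**The case against.** The strongest reply is that no stated decision changes. The decision rule uses cell comparisons, all of them estimable, and no section names an averaged menthol effect as an estimand. The menthol hypothesis in 4.1 can be tested with differences between administered cells. Objective 4.3 can be read as menthol with each coolant in turn, which the data support. All of this stands. It does not rescue the model sentence, which lists all three factors with all interactions.

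It is also fair that a main effect depends on coding in any interaction model, even with every cell filled. The no-coolant effect and the mean over six administered conditions are both legitimate and would still differ after the fix. Only the negatively weighted value comes from the empty cells. It needs sum-to-zero coding, dropped columns and an analyst who reports it. The plan specifies no coding and no handling of aliased terms, so the artefact is possible, not planned.

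A reader might infer from the literal wording of 4.2 that the coolants are in fact mixed and the cells filled. The counts of 18 liquids and six bouts per session rule that out.

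**Conclusion.** The model in 6.4.1 and 6.5.1 is wrong as written, with low to moderate consequence. Eighteen of its 36 df before time, and 18 × (T − 1) more with time, have no data. The WS-3 × WS-23 part of the interaction objective cannot be tested, and effects averaged over the full grid are not estimable.

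A reader might go further and conclude that the primary analysis is undefined, that power is lost, or that the secondary objective fails as a whole. The documents do not support this. The primary contrasts are differences between administered liquids, the 80% power figure reproduces without reference to the empty cells, and 10 df of menthol-by-coolant interaction remain estimable. The documents likewise do not show that a distorted menthol effect will be reported; its size is unknown and is zero if menthol and coolant do not interact.

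The conclusion rests on Table 2 and the 18-liquid count being correct, which sections 5.1, 6.1.1 and 6.3 bear out.

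**What to change.** - In 6.4.1 and 6.5.1, replace the WS-3 and WS-23 factors with one six-level coolant factor (none, WS-3 low, WS-3 high, WS-23 low, WS-23 high, WS-23 4%) crossed with menthol. Deleting every term that contains WS-3 × WS-23, including those with time and menthol, is equivalent.
- Keep time within lab on its present terms, define its levels, and state how contrasts are averaged over it.
- Define each primary contrast as cell (coolant k, menthol m) minus cell (none, menthol m).
- Define any reported menthol effect over administered liquids only: at no coolant, or averaged over the six conditions.
- State in 4.1 and 4.3 that menthol with WS-3 and menthol with WS-23 are examined separately, and that a WS-3 × WS-23 interaction cannot be tested.
- Reconcile the wording of 4.2 with the 18 liquids in Table 2.

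The cost is an amendment to protocol and SAP wording. The data collected, the sample size, the primary contrasts and the stated power do not change.

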## 4 Study Objectives

### 4.1 Hypothesis

We aim to examine the impact of cooling components of WS-3, WS-23, and menthol on the appeal and addiction potential of nicotine-containing e-liquids among adults. We hypothesize that any addition (low, high) of WS-3, WS-23, or menthol will result in similar increases in addiction potential, and that when WS-3, WS-23, and menthol are combined they will produce additive effects relative to menthol alone. We also hypothesize similar changes in appeal outcomes.

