#### **6.1.3 Method of Assignment/Randomization**

Participants will be randomized to order of menthol conditions and WS-3 or WS-23 conditions.

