#### **6.1.6 Storage Conditions**

In order to ensure that we have adequate amount of e-liquid, of the same constituency, we will purchase large enough quantities of ingredients to create e-liquids for the entire study prior to starting these experiments which will be stored at and dispensed at Yale IDS Pharmacy. All raw ingredients (nicotine, propylene glycol, vegetable glycerin, flavorants) will be stored unopened in a locked cool and dry place onsite until recruitment begins.

Ingredients will be transported to Yale IDS Pharmacy prior to recruitment start. Once recruitment begins and e-liquids are needed, Yale Pharmacy will dispense e-liquid in 30mL batches. Once complete, e-liquids will be immediately transported to Pierce Labs, which is a secure building accessible only by key code, where they will be delivered and stored in appropriate light/temperature conditions. E-liquids will be delivered and stored in a controlled and dark laboratory environment housed in John Pierce Labs and/or West Campus Research Center. Pods will be filled with e-liquid mixtures at John Pierce Labs.

On the day prior to the lab sessions, a research assistant/associate/fellow who is not involved in the actual conduct of the lab sessions will fill the e-cig pods with the appropriate doses. The information on randomizations to menthol, WS-3, and WS-23 condition orders for lab sessions will be generated by study biostatisticians prior to study start. This information is stored on a randomization sheet that has each participant's information. The individual filling the pods will be notified of which subject ID number needs to be filled. Each 30mL bottle of e-juice will be shaken vigorously prior to filling the pods. Next, they will open the top of the pod and using a mechanical pipette will load 0.9ml into the pipette from the e-juice bottle and carefully transfer it into the pod for the main study (0.5ml will be loaded to the pods for the pilot study). Each pod is then stored in a separate airtight bag to avoid cross contamination of flavors. The individual bags are then stored together in a larger bag labeled with the study ID number and stored back in the container until the lab is set to begin. Once the research assistant is ready to begin each lab, they will open the container, take the appropriate pod(s) out and leave the others. At the end of the lab, they will return the pod(s) used that day to their proper bag and again return it to the box.

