In the main study session, participants will engage in a 15-min training session of the psychophysical tasks they will use to report sensory experience at Lab 1. For Labs 1-3, participants will engage in six directed puffing bouts (5 puffs/3 sec puffs/30 second interpuff intervals) will be separated by 30 mins to allow any sensory effects to dissipate between exposures, a procedure adapted from [name] previous studies. Puffing will occur using a puff topography device (i.e., an established device in which the e-cigarette is attached to a mouthpiece) to measure the parameters of each puff taken (puff duration, volume, etc.). During the 15-minute training session at Lab 1, participants will familiarize themselves with vaping using a puff topography device. Following bout, participants will complete in the following order measures of overall liking/disliking, intensities of sweetness, bitterness, cooling, and irritation/harshness, and where irritation/harshness is felt (i.e., mouth, throat, both). Sensory measures will be followed by collection of general appeal and reinforcing efficacy measures, and a post-exposure measure of craving (collected 15-min after exposure). Cardiovascular measures, including blood pressure and heart rate, will be recorded both before and after each bout session. Participants will be randomized to receive one of the 3 menthol conditions (no-menthol, low menthol, high menthol, levels determined by the pilot study above) in Lab 1 and will receive the alternative conditions in randomized order in Lab 2 and Lab 3. During each lab session the menthol condition will be paired with three WS-3 concentrations: no WS-3, low WS-3, or high WS-3 and three WS-23 concentrations: low WS-23, high WS-23, or 4% WS-23 (concentration determined by pilot study) in randomized order. E-cig pods containing e-liquids will be weighed before and after the session. Lab sessions will occur no more frequently than every 24-hrs. At the end of

each of the three lab sessions, participants will choose between the 6 e-liquids they sampled in the lab using a free-choice paradigm.

**Debrief:** Following study completion, participants will be thanked for their participation and will be given information from the CDC on cigarette smoking and e-cigarette cessation.

**Table 4.** List of Study Assessments

	Pre-screening	Intake (pilot)	Lab 1 (Pilot)	Intake (main)	Lab 1 (main)	Lab 2 (main)	Lab 3 (main)
Contact Info & Eligibility Review	X						
Informed Consent		X		X			

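### Menthol order is randomised across three lab visits, but the main-study model's only timing factor is time within lab; adding lab visit as a main effect is a free gain in precision.

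*Combined protocol and SAP*

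**What the plan says.** **Design.** In 5.1, 6.1.2 and 6.3, each main-study lab session pairs one menthol level with six coolant conditions. A participant is randomised to one menthol level in Lab 1 and "will receive the alternative conditions in randomized order in Lab 2 and Lab 3". Section 6.1.3 confirms this: "Participants will be randomized to order of menthol conditions and WS-3 or WS-23 conditions". Menthol therefore varies only between visits, and coolant varies within them. Under 6.1.6, "The information on randomizations to menthol, WS-3, and WS-23 condition orders for lab sessions will be generated by study biostatisticians prior to study start", so visit order will be on file for every participant.

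**Model.** Section 6.4.1 lists menthol, WS-3, WS-23 "and time within lab as factors, all interactions among those factors and adjust for stratification variables", and 6.5.1 repeats it: "and time within lab as factors, all interactions among those factors and adjust for stratification". Section 6.5.7 adds menthol cigarette status and, if needed, abstinence compliance. No model statement names lab visit, period or sequence.

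**Correlation.** Section 6.4.1 says: "A combination of random effects and structured variance-covariance matrices will be used to account for within-subject correlations". The structure is chosen by AIC. No candidates are listed and no lab-session term is named.

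**Hypothesis.** Section 4.1 expects that "any addition (low, high) of WS-3, WS-23, or menthol will result in similar increases in addiction potential".

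**The concern.** The plan models order inside a visit but not order across visits, although the latter is the level at which menthol is allocated. AIC is described only for the covariance structure, so that rule would not bring visit in as a fixed effect.

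The protocol gives some reason to expect Lab 1 to differ. Section 6.3 says that "participants will engage in a 15-min training session of the psychophysical tasks they will use to report sensory experience at Lab 1", and has participants get used to the topography device in the same training. This is only modest support, because 5.1 also starts every session with scale familiarisation and puff training.

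What is at stake is the precision of comparisons between menthol levels. The menthol main effect is one. Menthol versus none, needed for the similarity hypothesis in 4.1, is another. Both always compare different visits.

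**Working it through.** **Inputs from 6.4.2.** 60 completers, SD of paired differences 25, difference 11.4, alpha 0.01. (That section also prints an alpha of 0.1; only 0.01, two-sided, reproduces its power.)

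**The plan's own figure.** Noncentrality is 11.4/(25/√60) = 3.53 and the critical t on 59 df is 2.66. Power is 80.4%, against 80% stated. Both cells of each primary contrast fall in the same lab, so a visit effect cancels and this figure stands.

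**Assumptions, not in the documents.** Residual variance s = 25²/2 = 312.5. Session (lab-within-subject) variance g = 0.2s = 62.5, varied below. Drift across visits is d points per lab.

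**A. Leaving out lab visit, with a session term in the model**

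Per-subject variance of a difference between two menthol levels:

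- averaged over six coolant conditions: 2(g + s/6) = 2(62.5 + 52.08) = 229.2
- single cell: 2(g + s) = 750

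Under random order, two menthol levels are one visit apart with probability 2/3 and two apart with probability 1/3. Linear drift therefore adds d²(2/3 × 1 + 1/3 × 4) = 2d². A shift at Lab 1 only adds 2d²/3. The SE ratio is √(1 + added/base).

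| Drift per lab | Added | Averaged menthol effect | Single cell |
|---|---|---|---|
| 1 | 2 | √(1 + 2/229.2) = 1.004 | 1.001 |
| 3 | 18 | √(1 + 18/229.2) = 1.04 | 1.01 |
| 5 | 50 | √(1 + 50/229.2) = 1.10 | 1.03 |

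A Lab-1-only shift of 3 or 5 points gives 1.01 or 1.04 (averaged) and 1.004 or 1.01 (single cell).

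Sensitivity of the averaged effect at 5 points per lab: the loss runs from 20% to 6% as session variance goes from 2% to 50% of residual. If the SD of 25 came from differences across sessions (g + s = 312.5), the 4% and 10% become 5% and 12%.

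Power for an averaged menthol effect that has 80% with visit modelled, writing a for the SE ratio: Φ(2.80 − 1.96a) if orders are exactly balanced, Φ(2.80/a − 1.96) if simply randomised. The documents do not say which applies. At 3 points per lab this gives 78% or 77%, and at 5 points 74% or 72%. With balanced orders only the model's SE is inflated, so a nominal 5% test runs at 4.2% or 3.1%.

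**B. No session term in any candidate (conditional)**

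With a subject intercept only, the 17 within-subject df pool both sources, so the residual estimate is r = (17s + 12g)/17. The model SE of the averaged menthol effect is then √[(r/6)/(g + s/6)] times the correct one. At g = 0.02s the ratio is 0.95; at g = 0.5s it is 0.58.

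| Session variance, % of residual | 2 | 5 | 10 | 20 | 30 | 50 |
|---|---|---|---|---|---|---|
| Actual level of a nominal 5% test | 6% | 8% | 11% | 16% | 20% | 25% |

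The within-lab contrasts err the other way: their SE is too large by √(r/s), which is 3% at g = 0.1s and 16% at 0.5s.

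**The case against.** **The larger figures belong to a contrast that nobody named.** No hypothesis, objective or power statement names the menthol effect averaged over coolant conditions. The closest reading of 4.1 is menthol alone versus nothing, a single-cell contrast that moves by 3% or less in the table above. This stands and keeps the point small. The averaged effect is still the menthol main effect in the stated model.

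**The drifts are assumed and may be generous.** Five points per lab is 10 from Lab 1 to Lab 3, close to the 11.4 that the study is powered for. This stands too; at 1 point per lab the cost is negligible.

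**A reader might infer that menthol comparisons are biased, or that the primary test is compromised.** The documents do not support either. Order is randomised, so drift does not bias the contrast, and the primary contrasts compare exposures from the same visit.

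**A reader might also infer that the plan inflates type I error to as much as 25%.** It does not commit to a subject intercept alone. It promises random effects combined with structured covariance, chosen by AIC, and a lab-within-subject term is a natural candidate. In simulation with that term on offer, AIC picked it in 91% to 100% of runs for session variance of 10% to 50% of residual, and the error rate was 4% to 6%. Part B is a worst case under open wording.

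**A careless fix would not be free.** The plan takes all interactions among its listed factors, so visit must be kept out of that list. Requiring a session intercept in every candidate would also be redundant with exchangeable or unstructured within-lab covariances, which already contain it. Both objections are right and shape the fix.

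**Conclusion.** The point holds as a free improvement. It is not an error that threatens the trial. The stated model leaves out the visit at which menthol is allocated, and naming it is better at almost no cost. The consequence is lost precision in comparisons across visits: 0.4% to 10% on the SE of the averaged menthol effect and 0.1% to 3% on a single-cell contrast, for drifts of 1 to 5 points per lab with session variance at 20% of 312.5. Drift and session variance are both assumptions, and if there is no drift nothing is lost.

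That the term is absent from the written model is certain; how much it matters is not. The session-covariance point is secondary and applies only if no AIC candidate would otherwise allow for correlation within a session.

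**What to change.** 1. In 6.4.1 and 6.5.1, add lab visit (1 to 3) as a fixed main effect, and state that it is excluded from the interactions among the listed factors.
2. Secondary: state that every covariance structure compared by AIC allows extra correlation among observations from the same lab session, through either a lab-within-subject intercept or an equivalent within-lab block covariance, but not both.

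The cost is one or two sentences in two sections. Visit uses 2 df: with 60 completers, the 60 × 2 = 120 lab-level df less 2 for menthol leave 118, which become 116. Step 2 needs at most one further variance component. Sample size, visits and data collection do not change.
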